6.2.2.1. Procedure. Six biweekly sessions of MST will be conducted. Two VPA lists and two FNP lists will be used in each session. During MST, VPAs (e.g., "candle-table") or FNPs will be presented in horizontal arrangement on a computer screen at a rate of 1 per 6 seconds (this may be modified based on participant processing speed). For **VPA learning**, participants will be asked to generate a memorable sentence (first list) or form a distinctive mental image (second list) that links the two VPA items together. The therapist will help the participant generate sentences and images that are distinctive or unusual, and therefore more memorable. Specific examples of distinctive sentence-based and imagery-based encoding will be given (e.g., "The wax from the candle poured onto the table", or an image of a candle scorching a table) and will be developed as the treatment is manualized. Immediately following list presentation, the cue word will be presented without the target (e.g., "candle-_____") and the participant will be asked to generate the target. Spontaneous production of targets will be recorded. For each item not spontaneously recalled, participants will be asked to retrieve the

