sentence (first list) or image (second list) that they created during encoding, and will then be asked to retrieve the target word again. Unsuccessful retrieval will be initially cued by the therapist. Prompted recall will also be recorded. This procedure will be repeated five times for each list, each followed by a retrieval phase. For each session, the dependent measure is the percentage of correct target words (out of 12) in spontaneous and cued recall for each list during the final exposure trial. For **FNP learning**, we will use a training approach adapted from Hampstead³⁹ and Stringer⁹. Training teaches patients to self-generate cues linking faces and names; patients will also be provided cues to standardize procedures and to encourage strategy development. For each FNP, participants will be directed to a salient facial feature (a visual cue like a long nose) and given a nickname that rhymes with the actual name (verbal cue) linking the feature to the name. Patients will be instructed to associate the visual and verbal cues by creating mental images that emphasize or exaggerate the relationship between cues. After initial learning, FNP's will be repeated five times. On each presentation, participants will be asked to recall the visual cue, then the verbal cue, and then finally the name. Dependent measure is the percent correct recall of visual cues, verbal cues, and names on the final trial of each list.

6.2.3. Errorless Learning (EL). EL refers to a group of techniques that promote recovery of memory abilities using procedures that explicitly prevent the patient from making errors during learning¹⁰. EL is based on the premise that errors during training become primed in long term memory via implicit memory mechanisms relatively spared in amnesia⁴⁰. Because of impairment in explicit memory consolidation that would normally provide corrective influence, these errors exert an unusually strong detrimental effect on relearning. While the standard interpretation of EL is that implicit memory is responsible for the treatment effect^{41,42}, it has been more recently shown that the EL advantage results from residual, though impaired, episodic memory consolidation due to temporal lobe damage^{43,44}. EL has been shown to be a promising tool in memory rehabilitation^{15,40,45}, at least for individuals without severe executive deficits⁴⁶.

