6.2.3.1. Procedure. Six biweekly sessions of EL will be conducted, each using two VPA lists and two FNP lists. During EL, the word pairs (e.g., "candle-table") or face-name pairs will be presented in horizontal arrangement on a computer screen at a rate of 1 per 6 seconds with no encoding instructions. After initial presentation, the cue will be presented without the target. For VPA learning, the cue word in each pair ("candle - _____") will be presented, and the participant will be asked to provide the second (target) word, ***but only if they are certain they can retrieve it accurately. Guessing is explicitly discouraged.*** If the participant cannot provide the word within 3 seconds, the word appears on the screen for 3 seconds and the participant is asked to read the pair aloud. During training, each list will be presented five times in this fashion. The dependent measure is the percent correct target words produced (out of 12) during the fifth exposure trial for each list. The procedure will be repeated for the second VPA list and then for the two FNP lists, yielding 4 accuracy measures (percent correct) for each session.

6.2.4. Retrieval Practice (RP). Some authors have argued that practicing retrieval during learning is an essential feature of successful learning^{10,47}. Effects of RP are most robust when retrieval is effortful, successful and spaced over time^{48,49}. If retrieval of a learned item is practiced shortly after it is learned, but before it is forgotten, subsequent recall is enhanced, a phenomenon known as the "testing effect"⁴⁷. RP has been used recently to improve performance of memory-impaired patients with multiple sclerosis⁵⁰ and M-STBI^{11,19}.

6.2.4.1. Procedure. Six biweekly sessions of RP will be conducted. We will follow procedures outlined in Sumkowski et al¹⁹, who demonstrated efficacy of RP in a small group of patients with M-STBI and chronic memory deficits. For each session, two sets of 12 VPA's and 12 FNP's will be used. Paired stimuli will be presented together for 6s on a computer screen, and the participant will be asked to read the VPA or say the name (FNP) aloud. Following this, 3 6s filler pairs (other VPA's or FNP's) will be presented. Then, a 5s cued

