recall test (candle-_____), followed by a 1-s feedback screen (candle-table) will be presented, followed by another six 6s filler trials and another 5s cued recall test and 1s feedback. This continues until all 12 VPA's or FNP's are given. After VPA is complete, FNP is administered (counterbalanced). After a brief delay, the participant completes two separate delayed cued recall tests (VPA, FNP, counterbalanced). The procedure is repeated for the second set of VPA's and FNP's. Dependent measure: Percent correct scores on the delayed recall test for each of the two VPA and two FNP sets, recorded each session.

6.2.5 Manualization and Fidelity Testing. During Phase 1, session-by-session procedures, including instructions to therapists and patients, stimuli and stimulus presentation schedules, methods of data collection, and permissible procedural variations will be formalized into a treatment manual for each of the three interventions. Six Master's level therapists will be trained in all three interventions, and will practice administering them to volunteer participants. At the end of Phase 1, each therapist will administer each treatment to a Veteran participant with M-STBI. Each session will be video recorded for evaluation of treatment fidelity by the study team^{51,52}, which will review session recordings and will rate the degree to which the therapist adhered to the following aspects of the protocol: communication of content to the participant (consent, rationale for treatment, instructions for engaging in training), accurate use of cues, selection of stimulus materials, recording of data, and adherence to designated treatment schedules. We will develop a rating sheet that provides feedback to therapists on their adherence to the manualized protocol⁵³.

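### Each treatment's session score comes from a different test, and SAP 2.6 states no pooled match contrast that adjusts for treatment

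*Protocol*

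**What the plan says.** All three treatments use the same kinds of material, two 12-item lists of word pairs and two of face-name pairs per session (Protocol 6.2.1). The session score is defined separately for each:

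- **MST (6.2.2.1).** Word pairs: "the percentage of correct target words (out of 12) in spontaneous and cued recall for each list during the final exposure trial". Face-name pairs: "percent correct recall of visual cues, verbal cues, and names on the final trial of each list". At each face-name presentation "participants will be asked to recall the visual cue, then the verbal cue, and then finally the name".
- **EL (6.2.3.1).** "The dependent measure is the percent correct target words produced (out of 12) during the fifth exposure trial for each list". Participants are asked to answer "but only if they are certain they can retrieve it accurately. Guessing is explicitly discouraged".
- **RP (6.2.4.1).** "Dependent measure: Percent correct scores on the delayed recall test for each of the two VPA and two FNP sets, recorded each session". The delay is described only as brief.

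SAP 2.6 takes its Phase 3 variables from a Section 2.2, which I read as Protocol 6.2. It lists session-wise percent correct, post-treatment probes and 1-month probes. It compares matched with unmatched treatment person by person, using non-overlap, improvement rate and level, and Tau-U. Time-series regression and a last-day comparison are to be explored, with no terms given. The regression on severity names severity and deficit group, but neither treatment nor match.

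Hypothesis A (Protocol 5, Aim 2) is a general claim that matched treatment helps more. Table 4 assigns one person to each of four orders in each of three deficit groups. Protocol 6.5 also collects RAVLT, BVMT-R and the EON-MEM simulations before treatment, at the end of each treatment and at 1 month, as secondary outcomes.

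**The concern.** A within-person comparison of session scores always sets one test against another. The scores differ in prompting, in how sure the participant must be before answering, and in delay. Any level difference between tests enters the individual level, non-overlap and Tau-U results; Tau-U corrects for trend, not for a level offset.

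What this means depends on the question. If the aim is to see which treatment works better in one person, a general treatment advantage is signal. For Hypothesis A it is not, and a test-format offset is signal for neither. MST is always the matched score in the encoding group and RP always in the retrieval group, so one offset can look like a benefit of matching in one group and a harm in another.

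Table 4 balances constant offsets, but only a contrast over all participants uses that balance, and SAP 2.6 states none. The protocol intends to use these results to power a larger trial, which needs an interpretable estimate of the match effect.

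**Working it through.** **Inputs from the documents.** Table 4 orders (1 = MST, 2 = EL, 3 = RP); 6 sessions per treatment (6.4.2); 24 word pairs per session (6.2.1). The planned size reproduces: 3 groups x 4 orders x 1 person = 12. The documents give no recall rates, SDs, alpha or power, so every offset and SD below is assumed.

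**Step 1: where offsets go.** Let M, E and R be the constant offsets of the MST, EL and RP scores. Each person's matched-minus-mismatched difference is the match effect plus:

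| Deficit group | Two people | Two people |
|---|---|---|
| Encoding | M - E (orders 12, 21) | M - R (13, 31) |
| Consolidation | E - M (21, 12) | E - R (23, 32) |
| Retrieval | R - M (31, 13) | R - E (32, 23) |

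The 12 terms sum to zero. RP is in 8 of the 12 pairs. If only the RP test is 10 points harder, four people shift by +10 (two encoding, two consolidation), the four retrieval participants shift by -10, and four do not shift.

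**Step 2: size in one person.** Assume 60% correct, 24 items, 6 v 6 sessions, no trend and no match effect. By simulation, a test harder by 0, 5, 10 or 20 points gives a mean Tau (no trend correction) of 0.00, 0.27, 0.51 or 0.84.

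As a second yardstick, take offsets of d session-SDs and count people out of 12 expected to reach p<0.05 in each direction. Pattern A is MST +d, EL 0, RP -d, so MST and RP differ by 2d. Pattern B is RP -d only.

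| d | A, Tau-U | A, Mann-Whitney | B, Tau-U | B, Mann-Whitney |
|---|---|---|---|---|
| 0 (chance) | 0.21 | 0.25 | 0.21 | 0.25 |
| 0.25 | 0.35 | 0.43 | 0.26 | 0.31 |
| 0.5 | 0.77 | 1.0 | 0.40 | 0.49 |
| 1 | 2.2 | 2.9 | 0.97 | 1.3 |

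A t test on the difference in improvement rate stays at chance, 12 x 0.025 = 0.3, at every d.

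**Step 3: the pooled contrast.** Regress the 12 differences on match, period, MST and RP (EL as reference). The design has rank 4 and the match variance factor is 0.0833 = 1/12, the same as for a simple mean. Residual df are 12 - 4 = 8 instead of 11. By the noncentral t, the effect detectable with 80% power (two-sided 0.05) goes from 0.89 to 0.92 SD of the paired difference.

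- *Mean session score.* With an assumed between-person SD of the effect of 0.3, the SD of the difference is sqrt(2/6 + 0.3^2) = 0.651 session-SD; 0.89 and 0.92 become 0.58 and 0.60.
- *Improvement rate.* The squared deviations of sessions 1 to 6 sum to 17.5. With 0.3/2.5 = 0.12 as the between-person SD, the SD is sqrt(2/17.5 + 0.12^2) = 0.359, giving 0.32 and 0.33 session-SD per session.

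For a 0.5-SD match effect on the mean under pattern A, adjusted power is 0.65 at every d. A pooled test without treatment terms has power 0.68, 0.57, 0.30 and 0.01 at d = 0, 0.25, 0.5 and 1, and type I error 0.050, 0.027, 0.004 and 0.000. SAP 2.6 contains no pooled test, so this shows why the added test needs the treatment term; it is not a loss under the written plan. If the same 0.5 SD builds up at 0.2 SD per session (0.2 x 2.5 = 0.5), the adjusted improvement-rate test has power 0.40. If the benefit is fully present from session 1, that power is 0.05.

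**Step 4: what adjustment leaves behind.** Suppose the consolidation group loses an extra k points on the delayed RP test. RP is the mismatched treatment for two of its four members, so the pooled mean shifts by 2k/12 = k/6 (1.7 points if k = 10). The improvement rate shifts by 0.

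**Step 5: dropout.** Over all 66 ways to lose two of 12, the adjusted variance factor is 0.100 to 0.117. At offsets of +0.5, 0 and -0.5 SD, the unadjusted mean is biased by -0.20 to +0.20 SD.

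**The case against.** Several points on the other side stand.

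- **Same-format tests exist.** A reader might infer that nothing comparable is measured across treatments. Protocol 6.5 contradicts that, and SAP 2.6 lists post-treatment probes. But the 6.5 tests are secondary, and SAP 2.6 states no pooled match analysis for any measure.
- **Session scores may not be the measure for Hypothesis A.** Its stated primary measures are memory component performance, and Protocol 6.4.2 calls the word-pair and face-name tasks proximal outcomes. That session scores carry the test is my reading of SAP 2.6. The missing pooled contrast does not depend on it.
- **The tests are not wholly different.** Materials are shared, and MST and EL word pairs are both scored on the last trial of learning. Because the pairs are weakly associated, blind guesses would rarely score, so EL's rule affects mainly low-confidence recall. The clearest gap is the RP delay, nearest to pattern B, where the counts are smaller.
- **No per-person significance rule is stated.** The counts in Step 2 are a yardstick. They do not predict false claims under the plan.
- **This is a pilot in a single-case design.** Individual effect sizes suit it and should stay. They do not by themselves answer a general hypothesis.

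It is also tempting to say that the offsets would bias a pooled result. With all 12 completers constant offsets cancel exactly; without treatment terms the cost is precision, and bias only after unequal loss.

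**Conclusion.** Individual level, non-overlap and Tau-U comparisons of session scores mix test format and general treatment differences with the match effect, and SAP 2.6 states no pooled contrast that would use Table 4 to separate them. Improvement rate, already listed, is safe from constant offsets unless scores reach a ceiling.

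The size of the harm cannot be fixed from the documents. Under the assumed offsets, small ones do little (at 0.25 SD, 0.26 to 0.43 people per direction against 0.21 to 0.25 by chance) and large ones matter (at 1 SD, 0.97 to 2.9). A reader might conclude that the trial's individual results will be wrong; the documents do not support that, since they give no recall rates. Nor does the treatment term cure everything: on the mean score, an offset specific to one deficit group remains. Only section 2.6 of the SAP was available, so the statement about what is absent is limited to that section. The gap is worth closing because the repair is cheap.

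**What to change.** 1. In SAP 2.6, add a pooled match contrast over all participants with person, treatment (MST, EL, RP), period and match in the model. Name the primary summary in advance: improvement rate if robustness to constant offsets, including group-specific ones, is preferred; mean session score if power is preferred (0.65 v 0.40 in the example above). Report the other as supportive, and keep the individual effect sizes as descriptive.
2. For the cross-treatment comparison, score MST word pairs on unprompted targets ("Spontaneous production of targets will be recorded") and MST face-name pairs on names. Keep prompted and cue scores as process measures. This narrows the format gap without closing it: MST names still follow cue recall, and the RP test stays delayed.
3. Run the same contrast on RAVLT, BVMT-R and the EON-MEM simulations, using change over each treatment, as a like-for-like check on what treatment adjustment cannot remove. Their 1-month values follow both treatments, so they cannot be assigned to one.

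The cost is SAP wording and rescoring of recorded data, with no new testing, plus the three residual df and the slightly larger detectable effect shown in Step 3.

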6.3. Phase 2: Patient Characterization and Classification

6.3.1. Participants. Veterans aged 25-65 who are post-deployment, having served in OIF, OEF, or OND, who meet criteria for moderate or severe TBI during deployment, are eligible to participate. *Patients will meet the 2007 VA/DoD criteria⁵⁴, supplemented by data from the VA TBI Identification Semi-Structured Interview⁵⁵.* All patients will have gone through Level I and II assessments with positive findings. Inclusion/Exclusion criteria: *Primary inclusion criteria:* M-STBI (blast and blunt), \geq 6 months post-injury, no receptive aphasia (impairing ability to comprehend task instructions), able to participate in return visits. *Primary exclusion criteria:* No MRI contraindications, not claustrophobic, no current or past history of disabling Axis I psychiatric disorders (except for PTSD and depression), no active substance abuse, not pregnant.

6.3.2. Procedure. Phase 2 consists of three components. **First**, after informed consent is obtained, participants undergo **standardized neuropsychological screening** to characterize their neurocognitive deficits, enabling comparisons with other Veterans whose memory rehabilitation outcomes have been reported in the literature. **Second**, we will use an established neuropsychometric algorithm to **classify patients into process-specific groups** that locates their primary memory deficit at the encoding, consolidation, or retrieval stage. **Third**, we will conduct **high-resolution structural and resting state functional MRI (RS-fMRI)** to determine whether our group classification is associated with different neuroimaging signatures. In this pilot proposal, we will not evaluate pre-post structural or functional brain changes resulting from our interventions, though this will be a key feature of a subsequent MERIT proposal based on our preliminary outcomes here.

6.3.2.1. Pre-Treatment Neuropsychological Screening. Table 1 lists key neuropsychological measures. Participants will be offered \$50 for participation in neuropsychological screening.

Domain	Measure
Effort	Test of Memory Malingering (TOMM)
Intelligence	North American Adult Reading Test (NAART) Wechsler Abbreviated Scale of Intelligence (WASI 2-subtest)
Memory	California Verbal Learning Test II (CVLT-II) Rey Complex Figure Test (Meyers version) – includes forced-choice effort measure Logical Memory, Visual Reproduction I, II (WMS-III LM, VR)
Attention	WAIS-III Subtests yielding Working Memory Index (WMI); WMS-R DS
Processing Speed	WAIS-III Subtests yielding Processing Speed Index
Frontal/Executive	Controlled Oral Word Association Test (COWAT) – FAS, Animal Fluency Delis-Kaplan Executive Function System -Tower Test (DKEFS-Tower) Trail Making Test
Motor Speed and Dexterity	Finger Tapping Test (FTT) Grooved Pegboard Test (GPT)
Emotional/Psychiatric	PTSD Checklist-Military (PCL-M) Beck Depression Inventory

6.3.2.2. Classifying Participants into Process-Specific Groups

We aim to identify M-STBI patients whose injuries produce primary deficits in encoding/acquisition, consolidation/retention, or retrieval. While we expect that many patients may have some problems in more than one domain, many studies have concluded that memory problems after M-STBI are *primarily* rooted in one of these domains at the individual level^{5-7,56,57}. Three studies^{4,7,58} report distinct deficit patterns attributable to encoding, consolidation, and retrieval deficits using the CVLT⁵⁹. Crosson et al⁷ found that encoding deficits were marked by a high false positive (FP) rate and reduced hits on recognition, while consolidation deficits were marked by lower hit rates and lower FP (also see⁵⁸). Curtiss et al⁵⁶, using hierarchical clustering of CVLT and WMS-R variables, found three memory-impaired groups corresponding to acquisition/encoding, retention, and retrieval deficits. Millis and Ricker⁴ used Delis⁵⁹ six-factor solution of CVLT performance variance to identify patterns of verbal learning deficit after moderate-severe TBI. They found 4 identifiable clusters: a Disorganized type (n = 22; encoding deficit) who exhibited a haphazard learning style, elevated FP rate, reduced discriminability on recognition testing and increased susceptibility to proactive interference, an Active type (n = 15; retrieval deficit) who showed good semantic encoding, good acquisition rate, and disproportionate improvement on recognition (discriminability), a Passive type (n = 11; consolidation deficit) whose recall showed prominent serial position effects and rapid forgetting, and a Deficient type (n = 13; encoding deficit) who showed slow rate of learning, recency effects in free recall, and an excessively high FP rate on recognition. These results were subsequently replicated and extended³. We will use this classification scheme, summarized in Table 2. Deficient and Disorganized groups will be collapsed, as both suffer from encoding deficits. Characteristics of each class (encoding, consolidation, and retrieval) will be combined in multivariate fashion, creating a composite score. Participants will be assigned to the group corresponding to the most impaired composite score. We will also investigate other algorithms for classifying patients, with the goal of deriving the most accurate and stable method.

Table 2. Scheme for Classifying TBI patients into deficit categories.

Deficit	Encoding Deficit	Consolidation Deficit	Retrieval Deficit
Millis/Ricker/Deshpande Grouping	Disorganized (I) Deficient (IV)	Passive (III)	Active (II)
CVLT Factor Score Comparisons	Serial cluster <III, =II Primacy <III, =II Slope < II, =III FR Intrus =II, III List B v. A <II, =III	Serial cluster >I,IV,=III Primacy II Slope =I,IV, <II FR Intrus <IV, =II List B v. A =I,III,IV	Serial cluster =I, >III Primacy <III, =I,IV Slope >I,III,IV FR Intrus <III,=I,IV List B v. A >I, =III,IV
CVLT Performance Features	False pos >II,III Recency >II,III Recog Discrim <II,III	False pos <I,II,IV Recency <I Recog Discrim <I Semantic cluster <II SDFR v. Trial 5 >II	Semantic cluster >III,IV SDFR v. Trial 5 <III,IV FR Consist >I,IV Total (1-5) >I,IV List B >I,IV

6.3.2.3. Structural/Functional Neuroimaging. A long-term goal of our research is to provide evidence of neuroplastic changes after memory interventions by documenting treatment-related change in structural integrity and functional brain connectivity. In this study, we will collect pre-treatment MRI data to provide brain-based biomarkers of our 3-group classification. Participants will be offered \$50 for participation in each of two MRI acquisitions, once before treatment, and again 1 month post-treatemtn.

6.3.2.3.1. Acquisition Protocol. The MRI acquisition protocol is outlined in Table 3.

6.3.2.3.2. Structural MRI. Our laboratory uses tractography and tract-based spatial statistics^{60,61} along with reliable manual segmentation of memory-relevant grey matter structures to analyze structural damage after TBI. Fiber orientation is estimated using the Mixture of Wishart (MOW) distribution method⁶², capable of estimating fiber orientation in regions of crossing fibers. Tractography will be performed by seeding the whole brain with 64 uniformly-spaced seeds within each voxel. The tracking algorithm (based on FACT⁶³) creates **connectivity streamlines** using single and multi-fiber directionality. ROI's of key brain networks are defined anatomically and connected by streamlines. The streamlines with structural region masks will create a graph from which **network edge weight (NEW)**⁶⁴ will be computed. NEW controls for ROI surface area, seeding density, and voxel volume, and is a measure of network connection strength independent of image resolution, fiber length, and ROI size. NEW provides a quantitative measure of network connections that will be used together with FA and measures of radial and axial diffusivity to quantify structural brain integrity.

6.3.2.3.3. Resting-State Functional MRI. RS-fMRI, which measures intrinsic BOLD fluctuations in the absence of an explicit task, evaluates the degree to which activity in structurally connected brain regions co-varies (i.e., increases or decreases together) during rest. We will focus on resting state network connections between inferior frontal and medial temporal areas (shown to be prominent neural substrate of successful encoding^{65,66}) and other resting state networks, including default mode network (DMN), task-positive network (TPN), and

salience network (SN). The **DMN** consists of interconnected regions in the posterior cingulate cortex, medial and lateral parietal cortex, and medial prefrontal cortex, which show *deactivation* during active task conditions⁶⁷. The **TPN**, centered on connections between medial and dorsal regions of the frontal and parietal lobes, becomes more activated when the brain is presented with an attentionally demanding task⁶⁸; activity within this region during encoding is associated with accurate retrieval later on⁶⁹. The **SN**, comprised of dorsal anterior cingulate and the bilateral insula, responds to salient events and provides interaction between cortical, limbic, and subcortical structures essential for learning⁷⁰. M-STBI is associated with abnormalities in the DMN⁷¹⁻⁷⁴, TPN⁷³, and SN⁷⁵. It has been suggested⁷³ that TBI disrupts the normal segregation of

Table 3. MRI Protocol – UF AMRIS 3T Philips System; 32 Channel Head Coil
Total Scan Time = 43m 55s

Sequences	Purpose	Parameters
3D T1	Gray-white matter segmentation	176 continuous slices, voxel=1mm ³ , TR/TE=7.0/3.2ms, flip angle=8°, FOV=240x240mm, matrix=240x240x176mm, time: 4m 34s
3D FLAIR	Structural lesion identification, segmentation	180 continuous slices, voxel=1mm ³ , TR/TE=8000/338ms, IR=2400ms, flip angle=90°, FOV=240x240mm, matrix=240x240x180mm, time: 7m 12s
T2	Brain extraction	176 continuous slices, voxel=1mm ³ ; TR/TE=2500/363ms; FOV=240x240, flip angle=90°; matrix=240x240x165; time: 5m 27s
SWI	Micro-hemorrhage detection	Flow-compensated gradient echo; TR/TE1/ΔTE=59/8/6ms, FOV=240x192mm, flip angle=22°, matrix=240x192x170mm, voxel=1x1x2mm ³ , time = 5m 31s
HARDI	Fiber integrity, fiber modeling	74 continuous slices, 64 directions (1000s/mm ²), 6 directions (100/mm ²), voxel=2mm ³ , TR/TE=4840/86ms, flip angle=90°, FOV=224x224mm, matrix=224x224x140mm, time: 13m 1s
RS-BOLD	Resting state functional connectivity	36 slices, Single-shot EPI sequence, TR/TE=2500/30ms, flip angle=90°, FOV=252x252mm, matrix=72x72x36mm, slice thickness=3.5mm, voxel=3.5mm ³ , time: 8m 10s

the DMN and TPN through white matter damage to large corticortical pathways^{76,77} and through damage to pathways that link the SN with the DMN and TPN. Such abnormalities are related to memory dysfunction⁷³ and show experience-dependent improvements after memory training^{31,78}.

Participants will be asked to keep still during the entire scan to minimize motion artifacts. During resting state recording, participants will be asked to close their eyes, relax their body and mind, but not to fall asleep or focus on any specific thought. Total Interdependence (TI; developed by Co-I [name]), will be used to quantify the functional connectivity between pairs of ROIs. Compared with Cross Correlation (CC), which exploits the covariance structures of zero-lag data but ignores temporal relations that extend beyond zero-lag, TI estimates the total amount of mutual information between the two extracted BOLD time series⁷⁹. The statistical treatment of TI is similar to that applied CC estimates, but it has been shown that, by revealing additional temporal relationships not captured by CC, TI reproduces more precise task activated networks, and provides greater sensitivity in correctly deciding network membership⁷⁹.

